The study population will consist of male and female patients >28 days and confirmed TRAPS (cohort 1), HIDS (cohort 2), or crFMF (cohort 3).

It is aimed to randomize a total of 180 patients (60 per cohort, 30 per treatment arm) in approximately >20 centers worldwide. Since a 20% screening failure rate is expected, it is estimated that approximately 225 patients have to be screened.

The following patient populations will be screened at Day 1 and directly entered into the open-label treatment arm of the randomized withdrawal epoch (Epoch 3) at Day 113:

- TRAPS patients previously participating in clinical study CACZ885D2203 or the subsequent MPP treatment plan CACZ885D2207M (at most 19 patients).

In addition, the following patient populations will be screened and will enter into the open-label treatment arm of the Epoch 2 at Day 1:

- Male and female patients >28 days but <2 years old with bodyweight ≥ 3.75 kg
- Approximately 5 Japanese crFMF patients with non-exon 10 mutations otherwise fulfilling all the mandatory inclusion and exclusion criteria.

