Safety data for the subgroup of canakinumab naïve Japanese crFMF patients with non-exon 10 mutations, and patients >28 days but <2 years old, collected in Epoch 2, 3 and 4 will separately be reported from the other patients who will be screened and randomized in Epoch 2. Summary statistics for continuous variables will include N, mean, standard deviation, minimum, lower quartile, median, upper quartile, maximum. Summary statistics for discrete variables will be presented in contingency tables and will include absolute and relative frequencies.

If not otherwise specified, p-values will be presented as two-sided p-values and two-sided confidence intervals will be displayed.

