- a. A screening epoch to assess patients' eligibility of up to 12 weeks duration (Epoch 1)
- b. An open-label epoch of 16 weeks (Epoch 2)
- c. An open-label epoch of 24 weeks (Epoch 3)

- d. An open-label treatment epoch of 72 weeks to collect long-term safety data for canakinumab (Epoch 4)

All data will be analyzed separately for each independent cohort (TRAPS, HIDS, crFMF).

The purpose of the study is to provide evidence supporting answers to following questions. The data will be analyzed by Epoch:

1. Whether canakinumab at a starting dose of 150mg s.c. (or 2mg/kg for patients ≤ 40 kg) administered every 4 weeks is able to induce and maintain a clinically meaningful reduction of disease activity defined as resolution of the index flare at Day 15 and no new disease flares over 16 weeks of treatment in a greater proportion of patients with TRAPS, HIDS, or crFMF compared to placebo (Data from Epoch 2)
2. Whether, in patients responding to the initial dosing regimen of every 4 weeks, canakinumab will maintain its clinical efficacy if administered at a reduced dosing interval of 150mg s.c. (or 2mg/kg for patients ≤ 40 kg) every 8 weeks. (Data from epoch 3 and 4)

Safety data for the subgroup of patients coming from ACZ885D2203 and/or the subsequent Multiple Patient Program (MPP) treatment plan CACZ885D2207M collected in Epoch 3 and 4 will separately be reported from the other patients who will be screened and randomized in Epoch 2.

Safety data for the subgroup of canakinumab naïve Japanese crFMF patients with non-exon 10 mutations, and patients >28 days but <2 years old, collected in Epoch 2, 3 and 4 will separately be reported from the other patients who will be screened and randomized in Epoch 2.

Summary statistics for continuous variables will include N, mean, standard deviation, minimum, lower quartile, median, upper quartile, maximum, and number of patients with non-missing data (n). Summary statistics for discrete variables will be presented in contingency tables and will include absolute and relative frequencies.

If not otherwise specified, p-values will be presented as two-sided p-values and two-sided confidence intervals will be displayed.

All listings will be presented by cohort and treatment sequence.

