The cut-offs of 2700mg, and 5400mg were decided based on all options for cumulative dose over 72 weeks depending on the number of flares and initial dose regimen at start of epoch 4. The first group could be considered as patients taking initially 150mg q8w at start of epoch 4 with or without flare over 72 weeks, the second one grouping patients taking initially 150mg q4w or 300mg q8w at start of epoch 4 with or without flare over 72 weeks and the last one patients taking initially 300mg q4 with or without flare over 72 weeks.

Roll-over patients from ACZ885D2203/ CACZ885D2207M and naïve Japanese crFMF patients with non-exon 10 mutations and patients >28 days but <2 years old

Data for the subgroup of patients coming from ACZ885D2203 and/or the subsequent Multiple Patient Program (MPP) treatment plan CACZ885D2207M collected in Epoch 3 as well as canakinumab naïve Japanese crFMF patients with non-exon 10 mutations and patients >28 days but <2 years old collected in Epoch 2 and Epoch 3, will separately be reported from the other patients who will be screened and randomized in Epoch 2. For subgroup 1: Roll-over patients from ACZ885D2203/ CACZ885D2207M:

In epoch 3, for this subgroup of patients safety and efficacy data will be tabulated as follows:

----- Cumulative dose in mg over 24 weeks -----
<600mg 600mg - <1200mg $\geq 1200\text{mg}$

In epoch 4, this subgroup of patients will be reported together with the other patients as follows:

----- Cumulative dose in mg over 72 weeks -----

<2700mg \geq 2700mg- <5400mg \geq 5400 mg

For subgroup 2: Naïve Japanese crFMF patients with non-exon 10 mutations and patients >28 days but <2 years old:

Patient Demographics & other baseline characteristics and Adverse events data for this subgroup will be tabulated under one treatment group ACZ885. All other safety and efficacy data will be listed under one treatment group ACZ885 in epoch 2 and epoch 3. This subgroup of patients will also be reported together with the other patients in epoch 4 using same cumulative dose categories.

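### SAP 1.3 merges the roll-over TRAPS patients, and apparently the other non-randomized patients, into the Epoch 4 safety tables, although SAP 1.1 and Protocol Section 9 promise separate Epoch 4 safety reporting

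*SAP*

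**What the plan says.** Two sections set one rule, and a third sets another.

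- **SAP 1.1, roll-over TRAPS patients.** Their safety data "collected in Epoch 3 and 4 will separately be reported from the other patients who will be screened and randomized in Epoch 2". Protocol Section 9 (Data analysis) says the same.
- **SAP 1.1, Japanese non-exon-10 crFMF patients and children over 28 days but under 2 years.** Their safety data "collected in Epoch 2, 3 and 4 will separately be reported from the other patients". Protocol Section 9 agrees: data "collected in Epoch 2, 3 and 4 will separately be reported from the other patients who will be screened and randomized in Epoch 2".
- **SAP 1.3, opening sentence on these subgroups.** Separate reporting is limited to Epoch 3 for roll-overs. For the second subgroup it covers data "collected in Epoch 2 and Epoch 3, will separately be reported from the other patients who will be screened and randomized in Epoch 2". Epoch 4 is named for neither.
- **SAP 1.3, roll-overs in Epoch 4.** "In epoch 4, this subgroup of patients will be reported together with the other patients as follows", followed by the three cumulative-dose categories (below 2700 mg, 2700 to below 5400 mg, 5400 mg and above).
- **SAP 1.3, second subgroup in Epoch 4.** "This subgroup of patients will also be reported together with the other patients in epoch 4 using same cumulative dose categories".

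SAP 1.13.1 (adverse events), 1.13.3 (laboratory data) and 1.13.4 (vital signs) all take their treatment groups from section 1.3. Protocol Section 4 puts the number of roll-overs at "at most 19 patients" and the Japanese patients at about 5. It gives no number for the youngest children.

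**The concern.** Epoch 4 is the 72-week open-label epoch whose stated purpose is long-term safety. Protocol 2.3 also lists, as an exploratory objective, the safety and efficacy of canakinumab in exactly these non-randomized and roll-over groups. Because the safety sections point to SAP 1.3 for their groups, a programmer would follow 1.3 rather than 1.1. The separate Epoch 4 safety results would then be missing for the roll-overs, and possibly for the other subgroup.

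The roll-overs also differ from the randomized patients on facts in the protocol. They come from an earlier canakinumab study or its follow-on treatment plan (Protocol 4.1.2, criteria 8 and 9). They are exempt from the three-month canakinumab washout (Protocol 4.2, criterion 1c). They enter at Day 113 without passing through Epoch 2. A reader of a merged TRAPS table could not tell how much of it describes patients first treated in this trial.

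**Working it through.** **1. The rules side by side (safety data)**

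| Subgroup | Protocol 9 and SAP 1.1: separate in | SAP 1.3: separate in | SAP 1.3: Epoch 4 |
|---|---|---|---|
| Roll-over TRAPS | Epochs 3, 4 | Epoch 3 | together with the others |
| Japanese non-exon-10 and under 2 years | Epochs 2, 3, 4 | Epochs 2, 3 | together with the others, but the wording is open |

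For roll-overs no sentence in SAP 1.3 leaves room for a separate Epoch 4 table. For the second subgroup two features do. The sentence that tabulates adverse events under a single ACZ885 group carries no epoch limit, and the word 'also' in the Epoch 4 sentence can mean 'in addition'. Against that, the opening sentence of the same part confines separate reporting to Epochs 2 and 3.

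**2. How much follow-up is affected**

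Epoch lengths from Protocol 3.1 are 16, 24 and 72 weeks.

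- Roll-overs: 72/(24 + 72) = 72/96 = 75% of planned study time.
- Second subgroup: 72/(16 + 24 + 72) = 72/112 = 64%.

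**3. Share of added patients in the Epoch 4 cohort**

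With *m* added patients and *n* randomized patients entering Epoch 4, the share is w = m/(n + m). Protocol Section 4 gives 60 randomized patients per cohort. The values of *n* below 60 are assumptions.

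- TRAPS, m = 19: n = 60 gives 19/79 = 24.1%; n = 45 gives 19/64 = 29.7%; n = 30 gives 19/49 = 38.8%.
- crFMF, m = 5 Japanese patients: n = 60 gives 5/65 = 7.7%; n = 45 gives 5/50 = 10.0%.
- Three cohorts combined, children under 2 not counted: 24/204 = 11.8% at n = 180; 24/159 = 15.1% at n = 135.
- Children under 2: number not stated. If 1 to 10 joined one cohort of 60 (assumption), 1/61 = 1.6% to 10/70 = 14.3%.

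These are shares of a cohort. The Epoch 4 columns are cumulative-dose categories, and the share within any one column cannot be worked out from the documents.

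**4. Effect on an event rate**

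Let R be the subgroup's event rate divided by that of the randomized patients. With equal follow-up per patient, pooled rate / randomized rate = 1 − w + wR. The documents do not give R, so it is varied from 0.5 to 2.

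| R | TRAPS, w = 24.1% | crFMF, w = 7.7% |
|---|---|---|
| 0.5 | 0.88 | 0.96 |
| 1 | 1.00 | 1.00 |
| 1.5 | 1.12 | 1.04 |
| 2 | 1.24 | 1.08 |

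Merging can lower the rate, leave it unchanged or raise it.

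**The case against.** The best defence is that a pooled safety display is foreseen: Protocol 3.2 says that safety will be evaluated both within cohorts and at a pooled level. That stands, and a merged table is not in itself a breach. It does not replace the separate reporting that Protocol Section 9 and SAP 1.1 promise; the gap is the missing separate output. The promise also covers safety data only, so merging Epoch 4 efficacy data contradicts nothing, and no primary or secondary efficacy test is touched.

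The ambiguity for the Japanese patients and young children also stands. SAP 1.3 may intend a separate adverse event table in Epoch 4 as well, so for them the plan needs clarifying and the loss is not established.

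Three stronger readings are tempting, and the documents do not support them.

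- **That merging dilutes the long-term event rates.** No subgroup event rate is given, and the table in the working goes both ways. Randomized patients reach Epoch 4 only after 16 + 24 = 40 weeks in the study, so they too are selected for staying in it.
- **That roll-overs are selected for response.** Criteria 8 and 9 ask for completion of the earlier study and/or current participation in the treatment plan on a stable regimen. Neither requires a response.
- **That the single ACZ885 group in Epochs 2 and 3 wrongly combines young children with Japanese patients.** Protocol Section 9 and SAP 1.1 themselves treat these patients as one subgroup. Splitting them would be a preference, not a correction.

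**Conclusion.** The contradiction is real and lies in the current text of both documents. For roll-over TRAPS patients it is clear: following SAP 1.3 would leave out a promised safety output covering 75% of their planned study time. For the second subgroup SAP 1.3 is ambiguous and should be made explicit.

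The size that can be stated is a share of patients. Roll-overs are about 24% of the TRAPS cohort in Epoch 4 if all 19 and all 60 randomized patients enter. The share is higher if fewer randomized patients do, which is likely because Protocol 3.1.3.1 takes placebo responders off study treatment after Epoch 2. It is lower if fewer than 19 roll-overs take part; 10 of them, for example, would be 10/70 = 14.3% beside 60 randomized patients. What the mixing does to event rates, in direction or in size, cannot be known from these documents.

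**What to change.** Amend SAP 1.3 to agree with SAP 1.1 and Protocol Section 9:

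- Present Epoch 4 safety for the randomized patients without the added subgroups.
- Add separate Epoch 4 safety tables or listings for (a) the roll-over TRAPS patients and (b) the non-randomized subgroup of Japanese non-exon-10 crFMF patients and children under 2 years. Listings are enough where numbers are very small.
- Keep any table that merges these patients with the randomized ones only as an addition, and label it as such.
- Reword the Epoch 4 sentence for subgroup (b) so that 'also' clearly means in addition to separate reporting.

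If the sponsor does intend merged reporting alone, SAP 1.1 should be changed to match, and the departure from Protocol Section 9 documented with its reason.

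The cost is a wording change and a few small outputs. No further data are needed, and no efficacy analysis changes. The one drawback is that some of the extra tables will hold very few patients and can only be read descriptively.

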1.4 Summary of the analyses

Table 1-2 Analysis by Epoch

Endpoint/analysis	Epoch			
	Epoch 2 (restricted to initial randomized treatment arms)	Epoch 2	Epoch 3	Epoch 4
Patient disposition	X	X	X	X
Demography & baseline characteristics	X	X	X	X
Medical history	X			
Previous & concomitant medication	X	X	X	X
Surgeries and medical procedures		X	X	X
Rescue medications	X	X	X	X
Study medication: duration of exposure	X	X	X	X
Proportion of responders at week 16	X			
Supportive analysis using SAA	X			
patients who achieve a PGA < 2 at Week 16	X			
Serologic remission at week 16	X			
Normalized SAA	X			
Responder in epoch 3 (only for canakinumab responder in epoch 2)			X	
CRP		X	X	X
PGA		X	X	X
PPGA		X	X	X
Physician's severity assessment of disease signs and symptoms over time		X	X	X
Fever		X	X	X
Blinded escape	X			
Time to new flare			X	
AIDAI	X	X	X	
SF-12	X	X	X	
CHQ-PF50	X	X	X	
SDS v3	X	X	X	
Total IL-1 β		X	X	X
Adverse events		X	X	X
Laboratory data		X	X	X
Vital signs		X	X	X
ECG		X	X	X

1.5 Patient demographics and other baseline characteristics

Summary statistics will be provided for demographic and baseline characteristics for the below treatment groups, and by epoch:

1. In Epoch 2, by initial randomized treatment arms (canakinumab 150mg sc q4w, placebo, all subjects) and according to treatment groups defined in [section 1.3](#)
2. In Epoch 3, according to treatment groups defined in [section 1.3](#)
3. In Epoch 4, according to treatment groups defined in [section 1.3](#)

Demographics for subgroup of patients coming from ACZ885D2203 and/or the subsequent Multiple Patient Program (MPP) treatment plan CACZ885D2207M enrolled in Epoch 3 as well as canakinumab naïve Japanese crFMF patients with non-exon 10 mutations and patients >28 days but <2 years old enrolled in Epoch 2, will be presented separately from the other patients who will be screened and randomized in Epoch 2.

The following common background and demographic variables will be presented:

Continuous variables:

- Age at Baseline
- Height at screening
- Weight at screening
- Body mass index (BMI) at screening
- Time since first symptoms (years)
- number of flares per year
- average duration of flare (days)
- local standardized CRP (mg/l) at baseline
- SAA (mg/l) at baseline

Categorical variables:

- Age categories ($\geq 2- < 4$, $\geq 4- < 6$, $\geq 6- < 12$, $\geq 12- < 18$, $\geq 18- < 65$, ≥ 65)
- Gender (Male/Female)
- Race (White, Black or African American, Asian, Native Hawaiian or other, Pacific Islander, Unknown, Other)
- Ethnicity (Hispanic or Latino, Not Hispanic or Latino, Unknown, Not reported)
- Prior use of any biologics (No/Yes)
- Prior use of Anakinra (No/Yes)
- Prior use of Tocilizumab (No/Yes)
- Prior use of Etanercept (No/Yes)
- Confirmed gene mutation (TNFRSF1A gene for TRAPS, MEFV gene exon 10 for crFMF, MVK gene for HIDS) (No/Yes)
- Active disease at maximum colchicine dose (for crFMF patients) (No/Yes)
- Intolerance to effective doses of colchicine (for crFMF patients) (No/Yes)

- Type of mutation (display the first 3 most common mutation types then the rest in “Other” category) and allele
- Physician’s global assessment of disease activity at baseline (None, Minimal, Mild, Moderate, Severe)
- Physician’s severity assessment of disease signs and symptoms at baseline (Absent, Minimal, Mild, Moderate, Severe) for TRAPS: skin rash, musculoskeletal pain, abdominal pain, eye manifestations, for HIDS: lymphadenopathy, aphthous ulcers, abdominal pain, for crFMF: chest pain, abdominal pain, arthralgia/arthritis, skin rash
- Patient’s global assessment of disease activity at baseline (None, Minimal, Mild, Moderate, Severe)

Body Mass Index (BMI) will be calculated using the following formula:

$$\text{BMI} = (\text{body weight in kilograms}) / (\text{height in meters})^2$$

1.6 Patient disposition

The number of patients screened will be presented. In addition, the reasons for screen failures will be provided in listing and will be tabulated. The number and percentage of patients in the randomized set who completed study epochs, and who discontinued the study prematurely (including the reason for discontinuation) will be presented by epoch, initial randomized treatment and treatment sequence (defined in [section 1.3](#)) and for all patients.

For each protocol deviation, the number and percentage of patients for whom the deviation applies will be tabulated over the study (not by epoch) and will be presented according to randomization treatment in epoch 2.

1.7 Medical history

Any significant prior or active medical condition at the time of signing informed consent will be coded using the MedDRA dictionary. These medical conditions will be summarized by primary system organ class and preferred term by initial randomized treatment groups in epoch 2 for the safety set.

1.8 Study medication

The exposure to investigational treatment (number of doses) and duration of exposure (days) during this study will be summarized by cohort, epoch, initial randomized treatment and treatment sequence (defined in [section 1.3](#)) and listed for the Safety Set.

Duration of exposure will be defined as the time from the first dose of study medication in that epoch to the last visit in the epoch (e.g., treatment epoch 2) +1 in days. For subjects who discontinue, the last visit in the corresponding treatment epoch will be taken into account.

For the final analysis, dose distribution from baseline to end of epoch 4 for each cohort will be displayed.

1.9 Concomitant medication

The number and percentage of patients taking prior/concomitant medication will be summarized by cohort, treatment group in each epoch and ATC class for the safety set. The number and percentage of patients with surgeries and medical procedures will be summarized by cohort, treatment group in each epoch and MedDRA preferred term for the safety set. Prior and concomitant medications will be summarized by treatment group in separate tables. Prior medications will be summarized by initial randomized treatment groups in epoch 2. Concomitant medications will be summarized by epoch and treatment groups (defined in [section 1.3](#)). Concomitant medication occurring in follow-up period after discontinuation of study will be listed but not summarized in tables.

Prior medications are defined as treatments taken and stopped prior to first dose of study treatment in epoch 2. Any medication given at least once between the day of first dose of randomized study treatment and the date of the last study visit will be a concomitant medication, including those which were started pre-baseline and continued into the period where study treatment is administered.

Rescue medications (Corticosteroids and NSAIDS) will also be separately summarized by cohort, epoch, initial randomized treatment and treatment sequence (defined in [section 1.3](#)) and ATC class.

Colchicine positive subjects, will be summarized using counts and percentages of subjects who took colchicine at baseline and stopped before or at the end of epoch 2 and subjects who started taking colchicine after day 1 and stopped before or at the end of epoch 2. Subjects will be defined as colchicine positive according to the following:

- Patient who took colchicine continuing after receiving 1st ACZ drug
- Patient who took colchicine after 1st dose of ACZ drug and stopped it after 4 weeks (>4weeks)

Colchicine information for crFMF cohort will be listed.

1.10 Efficacy evaluation

All efficacy evaluations will be performed on the full analysis set (FAS). For the overall analysis from baseline to epoch 4, patients who randomized to Placebo group at the beginning of epoch 2, only data after the first dose of ACZ885 will be included.

1.10.1 Analysis of the primary endpoint

1.10.1.1 Variable(s)

Each cohort (TRAPS, HIDS, crFMF) of the study will have its own primary efficacy variable analyzed separately and independently of the other cohorts. The primary efficacy variable of the randomized treatment epoch (Epoch 2) and for the overall study is the proportion of responders within each cohort, where a responder in epoch 2 is defined as a patient who has

resolution of its index disease flare at Day 15 and does not experience a new flare during the 16 weeks following randomization.

Resolution of the index flare (initial flare at the time of the randomization) is defined at the Day 15 visit as:

- PGA < 2 and CRP within normal range (≤ 10 mg/L) or reduction of $\geq 70\%$ from baseline

Absence of new flares over the first 16 weeks, where new flare is defined from the time of the resolution of the index flare as:

- Physician's Global Assessment (PGA) ≥ 2 , and
- CRP ≥ 30 mg/l

In the randomized treatment epoch (Epoch 2), patients needing dose escalation in the canakinumab arms, or escape from Placebo and receive open-label canakinumab, or are discontinued from the study due to any reason prior to evaluating the primary endpoint will be considered as non-responders. Local standardized CRP results shall be used for responder evaluation. For all visits, if local standardized CRP result is missing then the central standardized CRP result should be considered (except when patient discontinued)". Note: the central lab values have to be standardized before they are used for the analysis and standardized value shall be conducted based on the SI normal range of 0.0-10.0 mg/l. Values in the original measurement unit (OMU), denoted x have been transformed into standardized values, denoted xref, as $x_{ref} = 10 \times [(x - \text{minOMU}) / \text{rangeOMU}]$, where minOMU and rangeOMU are minimum value and range on the OMU respectively.

Patient receiving an add-on dose before day 15 will not be considered as having resolution of the index flare at day 15.

